To evaluate the efficacy of mandatory hiatal hernia repair (hiatoplasty) performed during gastric sleeve surgery in reducing the incidence of postoperative gastroesophageal reflux disease (GERD) in patients undergoing this procedure in a hospital specializing in bariatric surgery in Tijuana, Baja California.

Specific

Demographic characteristics and comorbidities in patients undergoing gastric sleeve with hiatoplasty: These patients usually have significant obesity, often accompanied by comorbidities such as type 2 diabetes, hypertension, sleep apnea, and gastroesophageal reflux disease (GERD). Demographic characteristics may vary, but the prevalence of obesity and its associated comorbidities is high in many regions, including Tijuana, Baja California.

Incidence of postoperative GERD in patients undergoing gastric sleeve with mandatory hiatoplasty: Hiatal hernia repair is often performed to reduce the risk of postoperative GERD by repairing a herniated hiatus during gastric sleeve surgery. However, the exact incidence of postoperative GERD can vary and depends on factors such as surgical technique, patient anatomy and postoperative management.

Comparison of postoperative complication rates, including GERD: Postoperative complications may include, but are not limited to, bleeding, infection, sleeve stenosis, and GERD recurrence. Comparison of complication rates between patients with and without mandatory hiatal hernia repair may provide insight into the effectiveness of this technique in mitigating specific risks.

Postoperative quality of life analysis: Postoperative quality of life can be significantly improved after bariatric surgery due to weight loss and improvement of comorbidities. Specific measures may include, but are not limited to, physical mobility, self-esteem, relief of symptoms of comorbidities, and overall satisfaction with the results of surgery.

Evaluation of the safety and technical feasibility of mandatory hiatoplasty: The integration of hiatal hernia repair into gastric sleeve surgery should be evaluated in terms of technical feasibility, safety, and effectiveness in preventing recurrence of hiatal hernias and GERD. This may involve analysis of complication rates, specific surgical techniques, and long-term.

MATERIALS AND METHODS

Research design

A retrospective case series will be performed.

Universe of study

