Electronic clinical records of patients over 18 years of age of indistinct gender who underwent gastric sleeve with hiataloplasty for obesity or overweight management in a hospital center specialized in bariatric surgery in Tijuana, Baja California.

Study period

March 2024 - July 2024.

Sample size

To calculate the sample size, the formula for prevalence studies for infinite populations was used, considering a confidence interval of 95% and a margin of error of 5%. The formula is presented below:

$$n = \frac{Z_{\alpha/2}^2 (p * q)}{d^2}$$

where,

$Z_{\alpha/2}$ = Z-score of a normal distribution $\alpha/2 = 1.96$

$p = 20\%$

$q = 100 - p = 70\%$.

d^2 = margin of error = 10

n= a minimum of 275 patients is required

Sampling

Non-probabilistic sampling will be used.

Inclusion and non-inclusion criteria

Inclusion criteria

- Patients over 18 years of age.
- Gender indistinct.
- Overweight, obesity grade I, II, III, super obesity or super-super obesity.

- Underwent gastric sleeve with hiataloplasty for obesity management at a high volume Tijuana hospital dedicated to bariatric surgery.

Non-inclusion criteria

- Patient records with incomplete information.

Description of the study

1. This study will be subject to review by the Research and Research Bioethics Committees of the hospital in question. Since this is a retrospective study, informed consent is not required.
2. After approval, the electronic clinical records of overweight and obese patients who meet the inclusion criteria and who underwent bariatric surgery for obesity management in Tijuana during the study period will be reviewed.
3. The following information of interest will be obtained from the file: age, sex, comorbidities, BMI, type of procedure, duration of surgery, final bleeding, immediate postoperative and transoperative complications. Patient follow-up information will also be obtained, which is obtained both in person for patients who can attend follow-up consultations and remotely by e-mail after sending a medical questionnaire and subsequent response from patients who reside in another city or country and therefore cannot attend their follow-up consultations in person.
4. Finally, the data will be captured in SPSS for statistical analysis.
5. To measure the quality of life of patients and the effectiveness of surgery, the Bariatric Analysis and Reporting Outcome System (BAROS) scale will be used.

Definition and operationalization of the study variables

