Variable	Conceptual definition	Operational definition	Measurement units	Type of Variable
Age	Years a person has lived since birth	Patient's age, recorded in the file.	Years	Quantitative
Sex	Difference in physical and sexual characteristics that distinguish men from women.	Classification of the patient as male or female	Male Female	Qualitative Nominal
Chronic comorbidities	Long-standing diseases directly related to obesity	Additional diseases recorded in the patient's record	None Diabetes mellitus Hypertension Cardiovascular GERD Dyslipidemia Hypothyroidism SAOS Depression Another	Qualitative Nominal
BMI	Universal unit for estimating the amount of body fat a person has.	BMI value recorded in the file, or calculated from weight and height, as: Weight (Kg)/ Size (m) ²	Kg/m ²	Continuous quantitative
Obesity level	Excess or a general excessive accumulation of fat in the body	Degree or level of obesity in the patient. Grade I: 30-34.9 Kg/m ² Grade II: 35-39.9 Kg/m ² Grade III: >=40 Kg/m ² Superobesity >50 Kg/m ² Super-super-obesity >60 Kg/m ²	I II III Superobesity Super-super-obesity	Qualitative ordinal
Duration of surgery	Time of the surgical process.	Time of surgery recorded in the file	Minutes	Quantitative
Trans-operative complications	Adverse events developed during surgery	Perioperative complications recorded in the record	None Bleeding Pneumothorax Organ injury Vascular injury Other	Qualitative Nominal
Postoperative complications	Adverse events developed after surgery	Postoperative complications recorded in the record or mentioned by the patient at follow-up	None GERD Bleeding Leakage Obstruction Diarrhea Embolism Other	Qualitative Nominal

STATISTICAL ANALYSIS

A database will be created in Excel, which will be downloaded into the statistical package SPSS v.26 in its MacOS version for data processing.

A descriptive analysis will be performed. For qualitative variables with frequencies and percentages. For quantitative variables, the descriptive analysis will consist of mean and standard deviation. In case quantitative variables have a non-parametric distribution, median and interquartile range will be used as descriptive statistics.

ETHICAL CONSIDERATIONS

The present research project was submitted to evaluation by the Local Health Research and Bioethics Committees for assessment and acceptance.

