APPENDIX 2. FOLLOW-UP FORMAT

Follow Up Questionnaire

Please answer the following questions based on the present or how you currently feel

Weight *

Texto de respuesta corta

Did you describe your weight in kilograms or pounds? *

- Kg
- Lbs

Please select the checkboxes that best describes your current conditions (if any) compared to before your surgery

If you don't have any medical conditions, please skip this question

	Aggravated	Unchanged	Improved	Resolved
Diabetes				
Hypertension				
Dyslipidemia				
Apnea				
Depression				
Anxiety				
Reflux				
Insomnia				

If you were taking medications, has there been any change in your medication consumption after your surgery? *

- I did not take any medication
- Yes, now I take a lower dosage and/or less medications
- No, there were no changes
- Yes, now I take a higher dosage and/or more medications

Please specify the medications and dosages you are currently taking

Texto de respuesta larga

Do you suffer from frequent diarrhea? *

- No
- Yes

Does your diarrhea require medication?

- No
- Yes

Do you have very foul-smelling flatulence? *

- No
- Rarely
- Occasionally
- Frequently

Do you have very foul-smelling stools? *

- No
- Rarely
- Occasionally
- Frequently

Have you suffered any fractures after your bariatric surgery? *

- No
- Yes

Where on your body and in what year did the fracture occur?

Texto de respuesta larga

Have you ever been told that you have thinner bones or osteoporosis? *

- No
- Yes

Quality of Life

Please answer the following questions based on how you currently feel

Usually, I feel... *

1 2 3 4 5

Very bad about myself

Very good about myself

I enjoy physical activities... *

1 2 3 4 5

Nothing at all

Very Much

I feel comfortable in social gatherings... *

1 2 3 4 5

Nothing at all

Very Much

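### The follow-up questionnaire does not prompt for most listed complications and the variable has no 'not assessed' level, so post-discharge events in patients followed only by e-mail are likely under-counted

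*Protocol*

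**What the plan says.** **Sources of data.** Under Description of the study, item 3, the file supplies "duration of surgery, final bleeding, immediate postoperative and transoperative complications". Follow-up comes from visits or, by e-mailed questionnaire, from "patients who reside in another city or country and therefore cannot attend their follow-up consultations in person".

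**The variable.** In the table of study variables, the operational definition is "Postoperative complications recorded in the record or mentioned by the patient at follow-up". The coding levels are "None GERD Bleeding Leakage Obstruction Diarrhea Embolism Other". There is no level for unknown, not asked or not assessed.

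**The follow-up form.** Appendix 2 is the only follow-up questionnaire shown. It tells patients to answer according to their present state. It covers weight, change in eight conditions including reflux, medication, bowel symptoms (for example "Do you suffer from frequent diarrhea"), fractures, bone thinning, quality of life, a reflux scale with two swallowing items, and satisfaction.

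**The in-hospital form.** Appendix 1 asks about complications during the stay, including leakage, hemorrhage, infection, intestinal obstruction, venous thromboembolism, dysphagia, re-intervention before discharge and a Clavien-Dindo grade.

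**The objectives that use these data.** The specific objectives say "Postoperative complications may include, but are not limited to, bleeding, infection, sleeve stenosis, and GERD recurrence". They also name "Comparison of complication rates between patients with and without mandatory hiatal hernia repair" and an evaluation of the safety of mandatory hiatoplasty.

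**The concern.** A complication treated elsewhere after discharge can reach the dataset of a remote patient in two ways: it gets into the hospital's record, or the patient mentions it. Appendix 2 gives the patient little occasion to mention it. It does not ask about most of the listed events, has no open question on complications, and directs attention to the present. A leak or embolism that was treated and resolved elsewhere falls outside that instruction.

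The variable then cannot separate a patient who was asked and had no event from one who was never asked. A percentage with both kinds in the denominator is not a clean complication rate, and how complete it is depends on where patients live. At stake are the complication-rate and safety objectives for the period after discharge. The main outcome, GERD, is prompted for and is not part of this point.

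**Working it through.** The protocol states no figure on this point, so there is none to reproduce. The check is a comparison of the forms item by item, followed by an illustration with assumed inputs.

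**Step 1. What each form asks.**

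| Event | Named in | Appendix 1 (hospital stay) | Appendix 2 (follow-up) |
|---|---|---|---|
| GERD | Variable table, objectives | Preoperative history | Yes: reflux scale, change in reflux |
| Diarrhea | Variable table | Yes | Yes |
| Bleeding | Variable table, objectives | Yes | No |
| Leakage | Variable table | Yes | No |
| Obstruction | Variable table | Yes | No; current swallowing symptoms only |
| Embolism | Variable table | Yes, as venous thromboembolism | No |
| Infection | Objectives | Yes | No |
| Stenosis | Objectives | Dysphagia only | Current swallowing symptoms only |
| Readmission, reoperation | Not a level of the variable | Re-intervention up to discharge | No |

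Of the six complications named in the variable table, the follow-up form prompts for two (GERD and diarrhea) and not for four. Infection, stenosis and reoperation would have to be coded as *Other*, for which there is no general prompt. The free-text fields concern medication and the site and year of a fracture.

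**Step 2. What can happen to an unasked event.** The protocol gives no coding rule, so three outcomes are possible:

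- It is entered as *None*. The post-discharge rate is then too low.
- It is left missing. The rate then depends on which denominator is used.
- The patient is dropped under the criterion on incomplete records, which does not define incomplete. Patients are then selected by place of residence.

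**Step 3. Size under the first outcome (assumed inputs).** Let t be the true rate of complications not prompted for, f the remote share, g the share of events that occur after discharge, and v the share of remote post-discharge events that are volunteered or already recorded. Assume that t and g are the same in remote and in-person patients, and that all other events are captured. Then

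observed rate = t × (1 − f × g × (1 − v)).

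With t = 5%:

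| f | g | v = 0 | v = 0.5 | v = 1 |
|---|---|---|---|---|
| 0.25 | 0.5 | 4.38% | 4.69% | 5.00% |
| 0.50 | 0.5 | 3.75% | 4.38% | 5.00% |
| 0.75 | 0.8 | 2.00% | 3.50% | 5.00% |

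For example, with f = 0.75, g = 0.8 and v = 0: 5% × (1 − 0.75 × 0.8) = 5% × 0.40 = 2.00%.

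For the post-discharge rate alone, g = 1 and the proportion lost is f × (1 − v). It runs from 0 (v = 1) to f (v = 0). With an assumed true post-discharge rate of 4%, the v = 0 end gives 3%, 2% and 1% for f = 25%, 50% and 75%.

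The protocol gives none of t, f, g or v. Within this model the rate cannot be overstated, because a missing prompt does not create a false event.

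**The case against.** A reader might infer that every unasked event is coded *None*, and hence that the overall safety rate is biased low by the remote share. The documents do not support that reading, for four reasons:

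- **No rule says so.** *None* is a level of the variable, but nothing assigns it to unasked items. Leaving them missing or excluding the record is equally compatible with the text, and handling of missing values may be set out in an analysis plan that is not shown.
- **In-hospital events are covered.** Appendix 1 asks about most of these events during the stay, with no distinction between local and remote patients. The gap is confined to the time after discharge.
- **Some later events may still be caught.** Swallowing symptoms are asked. A current medication may point to an event. A patient may tell the surgical team, or return to the hospital.
- **The contrast with in-person patients is not documented.** The protocol does not say outright that Appendix 2 is the e-mailed questionnaire, or that it is the only remote contact. Nor does it show a complication checklist for in-person visits.

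These points stand, and they remove any claim to a fixed size or a proven bias. They do not remove the gap. Appendix 2 is the only follow-up form shown, and treating it as the e-mailed one is the natural reading. The lack of prompts and of a not-assessed level is fixed in this protocol, and no later analysis can recover events that were neither asked about nor recorded. If in-person visits also lack a checklist, the problem is wider than the remote group.

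**Conclusion.** The point holds in a limited form. Appendix 2 does not prompt for bleeding, leakage, obstruction, embolism, infection, readmission or reoperation, and reaches stenosis only through current swallowing symptoms. The variable cannot record that an event was not assessed. Post-discharge complications in patients followed only by e-mail are therefore likely under-counted.

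The size cannot be derived from the protocol. For post-discharge events the shortfall lies between zero and the full remote share. The percentages in the working are illustrations; their v = 0 end assumes that nothing is captured in remote patients and everything in in-person patients. The conclusion rests on Appendix 2 being the questionnaire that is e-mailed. It affects the complication and safety objectives after discharge, not in-hospital complications.

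**What to change.** 1. Add a not asked/unknown code to the postoperative complications variable, and reserve *None* for patients in whom the events were assessed.
2. Report in-hospital complications on all patients. Report post-discharge complications separately, only on patients for whom these events were ascertained, and state that denominator.
3. State that remote patients are not excluded as incomplete on this ground.
4. Limit the safety conclusion to in-hospital complications unless post-discharge events were ascertained.
5. If questionnaires are still being sent, add a short checklist to Appendix 2: each complication in the variable table and objectives, and any readmission or reoperation at any hospital since discharge.

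Items 1 to 4 need no new data: one code, one split table and a narrower conclusion. The downside is a smaller denominator and a less favourable post-discharge rate. Item 5 may cost more. The Schedule of activities marks execution as completed, and the study is classed as risk-free because its data come from clinical records, so returning to patients who have already answered would be new data collection. If that is not possible, items 1 to 4 are enough.

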Vertical gastrectomy or popularly known as gastric sleeve can lead to a weight loss of up to 30% of body weight in the first postoperative year, with a smaller weight loss for up to 5 years (37).

In addition to the restrictive effect that results from removing a portion of the stomach, there are other mediators that are related to satiety and hypocaloric effects such as GLP-1 and Peptide YY (PYY) (38) as well as ghrelin, an orexigenic hormone that significantly reduces its levels due to the reduction of ghrelin secreting cells P-D1 that are found mostly in the gastric fundus (39). Also, gastric sleeve has effects on the microbiota that are believed to be related to weight loss through a reduction in caloric energy absorption (40).

The gastric sleeve has been shown to have the greatest improvement in metabolic risk compared to any other bariatric procedure (41-43). The metabolic risk markers that have benefited the most are: reduction of blood pressure, glycosylated hemoglobin and inflammatory markers, among others that have not yet been fully studied (44).

COMPLICATIONS ASSOCIATED WITH SLEEVE GASTRECTOMY

Bariatric surgery has become for many the best method to treat obesity, especially in severe cases and due to the multiple benefits obtained after this type of procedure; however, as with any major surgery, there is a risk of complications, and although in the bariatric field they are relatively uncommon, when they occur they may require a multidisciplinary management that is not simple (45).

Sleeve gastrectomy, as a leading technique in metabolic and bariatric surgery, has gained popularity for its effectiveness in achieving considerable weight loss in a short period of time. However, this procedure is not without complications. The most common complications include bleeding, nutritional deficiencies and leakage (46).

One of the most prominent chronic complications of gastric sleeve is the development of postoperative de novo gastroesophageal reflux disease (GERD),

which can range from esophagitis to more serious conditions such as Barrett's esophagus and esophageal cancer (47). The prevalence of GERD in the Western population is estimated at 7.7%, and its pathogenesis is multifactorial, involving factors such as hypotonia of the lower esophageal sphincter (LES), inadequate transient relaxations of the LES, and the contribution of hiatal hernia (48).

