The incidence of postoperative GERD in patients undergoing gastric sleeve surgery is a growing concern. The prevalence of GERD in the general population is considerable, and its occurrence or exacerbation after bariatric surgery represents a significant clinical problem. Moreover, the management of postoperative GERD involves additional costs for both the patient and the health care system, in terms of long-term medication, clinical follow-up and, in some cases, surgical reintervention. The complexity of this problem lies in the multifactorial nature of its etiology. Factors such as hypotonia of the lower esophageal sphincter and the presence of hiatal hernia contribute to the development of GERD. Therefore, it is imperative to explore surgical strategies that can mitigate this risk. One such strategy is mandatory hiataloplasty during sleeve gastrectomy, which, although not extensively investigated in this specific setting, has the potential to address one of the key etiologic factors of postoperative GERD.

However, the adoption of mandatory gastric sleeve hiataloplasty presents not only technical challenges, but also involves considerations of surgeon training, hospital resources, and acceptance of new surgical protocols. The need for a more preventive and comprehensive approach to bariatric surgery is clear, but requires a solid evidence base and adaptation of current surgical practices. This context raises a significant issue: should mandatory hiataloplasty be integrated into the gastric sleeve to reduce the incidence of postoperative GERD and improve long-term outcomes for patients undergoing bariatric surgery?

HYPOTHESIS

Alternative hypothesis

Mandatory hiatal hernia repair performed during gastric sleeve surgery significantly reduces the incidence of postoperative gastroesophageal reflux disease (GERD) compared to gastric sleeve performed without mandatory hiatal hernia repair.

Null hypothesis

Mandatory hiatal hernia repair performed during gastric sleeve surgery does not have a significant impact on reducing the incidence of postoperative gastroesophageal reflux disease (GERD) compared to gastric sleeve performed without mandatory hiatal hernia repair.

OBJECTIVES

General

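### Incidence of postoperative GERD is counted at unspecified times after surgery, so the reported percentage refers to no defined period

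*Protocol*

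**What the plan says.** The general objective is to evaluate efficacy in reducing the incidence of postoperative GERD. One specific objective is headed "Incidence of postoperative GERD in patients undergoing gastric sleeve with mandatory hiatoplasty". Neither names a period.

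In the table under Definition and operationalization of the study variables, GERD is one category of postoperative complications. Its operational definition is "Postoperative complications recorded in the record or mentioned by the patient at follow-up". Nothing in the table records time since surgery or length of follow-up.

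Other parts of the protocol that could supply a time anchor do not:

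- **Description of the study, item 3** collects "immediate postoperative and transoperative complications", plus follow-up information obtained in person or by e-mailed questionnaire. It gives no visit times and no sending date.
- **Inclusion and non-inclusion criteria** set no minimum follow-up. The only non-inclusion criterion is incomplete records, and incomplete is not defined.
- **Appendix 1** asks about GERD before surgery. Its postoperative part ends with the hospital stay, and the complication list there has no GERD item.
- **Appendix 2** opens with "Please answer the following questions based on the present or how you currently feel". The form as shown has no date, visit or months-since-surgery field.
- **Statistical analysis** reports qualitative variables as frequencies and percentages.

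The theoretical framework treats new reflux after sleeve gastrectomy as a chronic complication. The research question asks whether the procedure would "improve long-term outcomes for patients undergoing bariatric surgery".

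**The concern.** An incidence proportion has meaning only over a stated period. Here the counting rule itself pools unequal times at risk, because a case counts whenever it happens to be noted. It also mixes two kinds of information: events ever written in the record, which accumulate over time, and answers about how the patient feels today, which measure current prevalence.

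The percentage would then depend partly on how long after surgery each patient was last seen or wrote back. That interval may differ between patients seen in person and those who reply by e-mail. A reader could not place the figure beside a published rate at a known follow-up time, nor use it for the long-term question that motivates the study.

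**Working it through.** **No timed figure to reproduce.** The only expected proportion in the protocol is p = 20% in the Sample size section. It is not labelled as GERD and has no time point. It is used below only as an assumed anchor.

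**Possible follow-up intervals.** The protocol gives two surgery windows.

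- The Study period is "March 2024 - July 2024", and item 2 of the study description says that records of patients "who underwent bariatric surgery for obesity management in Tijuana during the study period will be reviewed". If data close in July 2024, follow-up runs from 0 to about 5 months.
- The abstract places surgery in March to June 2022. Assume assessment between April 2024 (execution in the Schedule of activities) and July 2024 (end of the study period). End of June 2022 to early April 2024 is about 21 months; early March 2022 to end of July 2024 is about 29 months.

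**Dependence on follow-up length.** Assume patients free of GERD at surgery and a constant rate that reaches 20% at T months. Then

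F(t) = 1 − exp(−λt), with λ = −ln(0.8)/T.

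For T = 12, λ = 0.2231/12 = 0.0186 per month. T is unknown, so 24 and 60 months are shown as well.

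| 20% reached at | 1 month | 5 months | 21 months | 29 months |
|---|---|---|---|---|
| 12 months | 1.8% | 8.9% | 32.3% | 41.7% |
| 24 months | 0.9% | 4.5% | 17.7% | 23.6% |
| 60 months | 0.4% | 1.8% | 7.5% | 10.2% |

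On the first row, the proportion changes by a factor of 8.9/1.8, about 4.8, across the 2024 window and by 41.7/32.3, about 1.3, across the 2022 window. The much larger gap between the two windows comes mainly from the conflict over surgery dates, which is a separate defect.

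**Direction.** GERD is a listed comorbidity in the variable table and is not an exclusion. Appendix 2 lets a patient report reflux as unchanged or aggravated. If a share b had GERD before surgery and all of them mention it, the counted proportion is b + (1 − b)F(t). The protocol quotes a 7.7% GERD prevalence for Western populations. Taking b = 7.7% purely as an example with T = 12:

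- 1 month: 0.077 + 0.923 × 0.0184 = 9.4%
- 5 months: 0.077 + 0.923 × 0.0888 = 15.9%

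Short follow-up therefore does not guarantee a low count. The distortion can go either way.

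**The case against.** **A separate analysis plan may fix the time point.** The time at which the main outcome is assessed is basic protocol content. This protocol does define its outcome variable and its analysis, and does so without time. The objection does not remove the point.

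**A reader might infer that the reported incidence will be close to zero because follow-up is short.** The documents do not support that. It needs the 2024 surgery window and patients free of GERD at baseline. The abstract gives the 2022 window, and patients with GERD before surgery are not excluded.

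**A reader might also infer that patients assessed at one month and at two years sit in the same percentage.** Neither surgery window produces that mix with assessment in 2024. It could arise only if earlier contacts already in the records are counted, and the protocol does not say whether they are. Under the 2022 window the spread is moderate.

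**The study is a descriptive series of patients who all had hiataloplasty.** No length of follow-up would let its percentage show that the procedure works, and fixing the time point does not cure this. That stands. The argument here is only that the percentage has no defined meaning as an incidence.

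**Long-term is not in the hypotheses or the general objective.** Correct. It appears in the research question and in an unfinished sentence of the specific objectives, so it carries limited weight. The missing period matters regardless.

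**Conclusion.** The point holds in a limited form. The main outcome has no assessment window, and the stated counting rule pools ever-recorded events with current-state answers at differing times after surgery. The resulting percentage is not an incidence over any period.

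Its size and direction cannot be determined from the protocol. They depend on which surgery window applies, on whether earlier contacts in the records count, and on how pre-existing GERD is handled. The figures of 2% to 9% (2024 window) and 32% to 42% (2022 window) rest on an assumed constant rate, an assumed 20% at 12 months and no GERD at baseline. They show sensitivity to follow-up length and do not predict the result.

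This should be fixed before the percentage is reported. It is not rated a must-fix, because within either surgery window the range of follow-up is bounded and the remedy is simple.

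**What to change.** 1. Reconcile the surgery window between the abstract and the methods. The attainable follow-up is unknown until this is done.
2. Capture the date of each follow-up contact, in person or by e-mail, and add months since surgery to the variable table. Appendix 1 has the surgery date. Appendix 2 as shown has no date field, so it cannot be assumed that questionnaire dates are already held.
3. Define the GERD outcome at one follow-up window that the reconciled cohort can actually reach. A 12-month landmark with a margin of 3 months (9 to 15 months) would overlap neither 0–5 nor 21–29 months, so it should not be adopted by default.
4. Include in the main table only patients assessed in that window. Report other contact times separately, with the distribution of follow-up.
5. If the reconciled window allows only a few months, restate the objective as early postoperative reflux and remove long-term from the research question and objectives.

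The cost is one captured date, one derived variable, revised wording, and a smaller main table because patients not assessed in the window drop out. The Schedule of activities marks execution as completed, so dates may have to be retrieved from visit notes and e-mail replies.
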